7.4.2 Analysis of Secondary Endpoints

7.4.2.1 Time to PSA Progression with 1st Line AAT + 2nd Line AAT (TTPP2)

TTPP2 is defined as the period from randomization to the date of PSA progression with 2nd line AAT. The total of time to PSA progression with 1st line AAT and time to PSA progression with 2nd line AAT will be evaluated. Convention of censoring is specified in Table 7-1.

The distribution of the TTPP2 will be estimated using the Kaplan–Meier method. The median TTPP2 will be estimated using the 50 percentile value of the Kaplan–Meier curve. The two-sided 95% CI will be calculated based on the estimation.

7.4.2.2 PSA Response Rate to 1st Line AAT (Decrease by at Least 50% or 90% from Baseline)

The PSA response rate decreasing by at least 50% will be calculated by treatment groups of subjects with baseline PSA value and PSA measured at least once at least 3 weeks passed after the lowest PSA. For the comparison of the response rate between the enzalutamide and flutamide groups, the stratified Cochran–Mantel–Haenszel test will be used. The stratification factor will be the disease stages (M0/N0, M0/N1, or M1) used as stratification factor for allocation.

PSA decrease by at least 90% will also be compared at the 0.05 significance level (two-sided) between the enzalutamide and flutamide groups using the stratified Cochran–Mantel–Haenszel test.

Response rate, its Clopper-Pearson exact confidence interval and its count within stratification will be summarized for each treatment. Mantel-Haenszel common risk difference for response (enzalutamide - flutamide) and its 95% confidence interval based on the variance claimed by Sato (1989) will be estimated.

Water fall plot will be made to present the percent change of PSA from baseline at the lowest PSA value (except within 3 weeks from baseline) for patient who have at least one time point PSA reduction in the 1st line AAT period, and the highest PSA value (except within 3 weeks from baseline) for patient who have never had PSA reduction, respectively.

7.4.2.3 PSA Response Rate to 1st Line AAT at Week 13 (Decrease by at Least 50% or 90% from Baseline)

The PSA response rate decreasing by at least 50% (or by at least 90%) will be calculated by treatment groups of subjects with baseline PSA value with 1st line AAT and PSA measured at week 13. The PSA response rate at week 13 will be assessed by the same method as that with the PSA response rate to 1st line AAT. Water fall plot will be made to present the percent change of PSA from baseline at Week 13 PSA value for each patient.

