7.1 Sample Size

The number of evaluable subjects will be approximately 200 subjects (1st line AAT enzalutamide group: 100, 1st line AAT flutamide group: 100).

The sample size to evaluate the time to PSA progression with 1st line AAT (TTPP1), which is the primary endpoint of the study, was calculated in consideration of the following points:

- Median TTPP1 with enzalutamide: 10.5 months.
- Median TTPP1 with flutamide: 6 months. Values reported in the literature: 5 months according to [Okihara et al., 2007], 6.25 months according to [Narimoto et al., 2010].
- The ratio of randomization of 1st line AAT enzalutamide and flutamide groups is 1:1.
- Subject enrollment period is 12 months, and the observation period is 24 months from the enrollment of the last subject.
- Type I error of the two-sided test is 0.05, and power is 90%.
- A log-rank test with the TTPP1 parameters shown above requires 135 events. The necessary number of subjects calculated based on the required number of events is 74 subjects per group.

Required number of events and necessary number of subjects above are calculated with the formulas below based on [Schoenfeld, 1983]. The codes in the formulas are defined as follows.

 M_t : Median TTPP1 in enzalutamide group

 M_c : Median TTPP1 in flutamide group

 t_a : Enrollment period

 t_f : Observation period from the last subject enrollment

 $Z_{1-\alpha}$: 1- α % point of standard normal distribution

 $Z_{1-\beta}$: 1- β % point of standard normal distribution

[figure not shown]
Hazard in enzalutamide group $(H_t) = \frac{\log_e 2}{M_t}$ Hazard in flutamide group $(H_c) = \frac{\log_e 2}{M_c}$ Hazard ratio for enzalutamide group/flutamide group $(HR) = \frac{H_t}{H_c}$ Required number of events $(N_d) = \frac{4 \times (Z_{1-\alpha} + Z_{1-\beta})^2}{(\log_e HR)^2}$ *The number after the decimal point will be rounded up to the nearest integer. Incidence of events of enzalutamide group $(P_t) = 1 - \frac{1}{6} \left(\exp(-H_t \times t_f) + 4 \times \exp\left(-H_t \times (t_f + \frac{1}{2} \times t_a)\right) + \exp\left(-H_t \times (t_f + t_a)\right) \right)$ Incidence of events of flutamide group

$$(P_c) = 1 - \frac{1}{6} \left(\exp\left(-H_c \times t_f\right) + 4 \times \exp\left(-H_c \times (t_f + \frac{1}{2} \times t_a)\right) + \exp\left(-H_c \times (t_f + t_a)\right) \right)$$

Incidence of events of both groups $(P) = \frac{1}{2} \times (P_t + P_c)$

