7.4.2 Analysis of Secondary Endpoints

7.4.2.1 Time to PSA Progression with 1st Line AAT + 2nd Line AAT (TTPP2)

TTPP2 is defined as the period from Day 1 of 2nd line AAT to the date of PSA progression with 2nd line AAT. The total of time to PSA progression with 1st line AAT and time to PSA progression with 2nd line AAT will be evaluated. Convention of censoring is specified in Section 7.10.

The distribution of the TTPP2 will be estimated using the Kaplan–Meier method. The median TTPP2 will be estimated using the 50 percentile value of the Kaplan–Meier curve. The two-sided 95% CI will be calculated based on the estimation. The benefit of enzalutamide as compared to flutamide will be descriptively assessed.

7.4.2.2 PSA Response Rate to 1st Line AAT (Decrease by at Least 50% or 90% from Baseline)

The PSA response rate decreasing by at least 50% will be calculated by treatment groups of subjects with baseline PSA value and PSA measured at least once after baseline. For the comparison of the response rate between the enzalutamide and flutamide groups, the stratified Cochran–Mantel–Haenszel test will be used. The stratification factor will be the disease stages (M0/N0, M0/N1, or M1) used as stratification factor for allocation.

PSA decrease by at least 90% will also be compared at the 0.05 significance level (twosided) between the enzalutamide and flutamide groups using the stratified Cochran–Mantel– Haenszel test.

7.4.2.3 PSA Response Rate to 1st Line AAT at Week 13 (Decrease by at Least 50% or 90% from Baseline)

The PSA response rate decreasing by at least 50% (or by at least 90%) will be calculated by treatment groups of subjects with baseline PSA value with 1st line AAT and PSA measured at Week 13.

The response rate between the enzalutamide and flutamide groups will be compared using the stratified Cochran–Mantel–Haenszel test. The stratification factor will be the disease stages (M0/N0, M0/N1, or M1) used as stratification factor for allocation.

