3.1.2 Secondary Objectives

- To determine the order of AAT treatment as assessed by time to PSA progression with 1st line AAT + 2nd line AAT (time to PSA progression 2 [TTPP2]).
- To determine the benefit of enzalutamide + ADT therapy as compared to flutamide + ADT therapy as assessed by PSA response rate to 1st line AAT (proportion of subjects with a decrease by at least 50% or 90% from baseline irrespective of the timing).
- To determine the benefit of enzalutamide + ADT therapy as compared to flutamide + ADT therapy as assessed by PSA response rate to 1st line AAT at Week 13 (proportion of subjects with a decrease by at least 50% or 90% from baseline).
- To determine the benefit of enzalutamide + ADT therapy as compared to flutamide + ADT therapy as assessed by time to PSA decrease by 50% from baseline with 1st line AAT.
- To determine the benefit of enzalutamide + ADT therapy as compared to flutamide + ADT therapy as assessed by time to treatment failure of 1st line AAT (time to treatment failure 1 [TTF1]).
- To determine the order of AAT treatment as assessed by time to treatment failure of 2nd line AAT (time to treatment failure 2 [TTF2]).
- To determine the benefit of enzalutamide + ADT therapy as compared to flutamide + ADT therapy as assessed by radiographic progression-free survival (rPFS).

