7.4.2.6 Time to Treatment Failure of 2nd Line AAT (TTF2)

TTF2 is defined as the period from randomization to the date of discontinuation of 2nd line AAT. Convention of censoring is specified in Table 7-1.

The distribution of the time to treatment failure of 2nd line AAT will be estimated using the Kaplan–Meier method. The median time to treatment failure of 2nd line AAT will be estimated using the 50 percentile value of the Kaplan–Meier curve. The two-sided 95% CI will be calculated based on the estimation.

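### The treatment-order objective (TTPP2, TTF2) has no planned between-sequence estimate, although the randomized design would support one

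*SAP*

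**What the plan says.** SAP 3.1.2 lists two objectives about sequence. One uses TTPP2; the other is "To determine the order of AAT treatment as assessed by time to treatment failure of 2nd line AAT". Protocol 2.1.2 has the same pair, and Protocol 1.1 gives the order of treatment as a reason for switching drugs after PSA progression.

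The planned analyses are short:

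- **TTPP2 (SAP 7.4.2.1):** "The distribution of the TTPP2 will be estimated using the" Kaplan–Meier method, with the median and a two-sided 95% CI.
- **TTF2 (SAP 7.4.2.6):** "The distribution of the time to treatment failure of 2nd line AAT will be estimated using the" Kaplan–Meier method, again with the median and its CI.

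Both are presented by planned treatment group in the ITT population (SAP 7.4), and SAP 7.1.2 defines treatment group as the randomized sequence. For both endpoints Protocol 7.4.2 adds: "The benefit of enzalutamide as compared to flutamide will be descriptively assessed". The SAP leaves that sentence out.

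**The concern.** The objective is comparative, but the planned output is one summary per group. A reader will see two curves and two medians, each with its own interval. No number will say how far apart the sequences are or how uncertain that difference is, and nothing adjusts the comparison for disease stage, the allocation factor used in the other stratified analyses.

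This is not how the SAP treats most of its comparative endpoints. TTPP1 and rPFS get a stratified log-rank test and a Cox model. PSA response gets a Mantel–Haenszel risk difference with 95% CI, and so do second-line PSA response and ORR, which are exploratory. At stake is a stated secondary question that could finish with usable randomized data and no effect estimate. The primary conclusion is not affected.

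**Working it through.** **1. The plan's own figures, and what they cover.** The inputs from Protocol 7.1 are "Median TTPP1 with enzalutamide: 10.5 months", "Median TTPP1 with flutamide: 6 months", two-sided 0.05, 90% power and 1:1 allocation.

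- Hazard ratio = 6/10.5 = 0.571, and ln 0.571 = −0.560.
- Events = 4 × (1.960 + 1.282)² / 0.560² = 134.2, rounded up to 135. This matches the plan.
- Event incidence with 12 months' accrual and 24 months' further observation is 0.858 (enzalutamide) and 0.966 (flutamide), mean 0.912. Subjects per group = 0.5 × 135 / 0.912 = 73.99, rounded up to 74. This matches.
- With 25% dropout, 74 / 0.75 = 98.7, or 99; the plan enrols 100 per group.

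All of this concerns TTPP1. No event count or target effect is given for TTPP2 or TTF2.

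**2. Contrasts specified, side by side.**

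| Endpoint (SAP section) | Between-group output |
|---|---|
| TTPP1 (7.4.1), rPFS (7.4.2.7) | Stratified log-rank test, Cox model |
| PSA response (7.4.2.2, 7.4.2.3) | Stratified CMH test, risk difference with 95% CI |
| Time to 50% PSA decrease (7.4.2.4), TTF1 (7.4.2.5) | Stratified log-rank test |
| ORR, exploratory (7.4.3.8) | Stratified CMH test, risk difference with 95% CI |
| **TTPP2 (7.4.2.1), TTF2 (7.4.2.6)** | **None** |

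**3. Precision of a sequence hazard ratio.** The event count D is an assumption. With 1:1 allocation, SE(log HR) = 2/√D, and the 95% CI is the HR multiplied or divided by exp(1.96 × 2/√D).

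| D | SE | CI factor |
|---|---|---|
| 80 | 0.224 | 1.55 |
| 100 | 0.200 | 1.48 |
| 120 | 0.183 | 1.43 |
| 150 | 0.163 | 1.38 |

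For a true 1.4-fold hazard ratio (ln 1.4 = 0.336), the chance that the 95% CI excludes 1 is about Φ(0.336/SE − 1.96). That is 54% at 150 events and 32% at 80.

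**4. Where TTPP2 might fall in that range.** As an illustration, give each drug its planning median in whichever line it is used, with exponential times and no switch gap. The hazards are 0.0660 and 0.1155 per month. The proportion without second progression is S(t) = (0.1155·e^(−0.0660t) − 0.0660·e^(−0.1155t)) / (0.1155 − 0.0660). This gives 0.395, 0.280 and 0.196 at 24, 30 and 36 months. Averaging over accrual as the plan does, the event proportion is 1 − (0.395 + 4 × 0.280 + 0.196)/6 = 0.715. That is about 106 events among 2 × 74 = 148 subjects, with a CI factor of exp(3.92/√106) = 1.46. With all 200 subjects and no dropout it is about 143. The censoring rules in Table 7-1 would lower both. TTF2 should have more events, because any discontinuation counts.

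**5. Are the endpoints defined well enough for a contrast?** TTF2 runs from randomization in Protocol 7.4.2.6 and SAP 7.4.2.6. TTPP2 is not settled:

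- Protocol 7.4.2.1 starts it at Day 1 of second-line treatment.
- SAP 7.4.2.1 starts it at randomization, but also calls it the total of the two progression times, as does SAP 6.1.2. That total leaves out the switch gap, which Protocol 2.2.1 allows to reach 6 weeks.
- Table 7-1 censors TTPP2 at treatment discontinuation without saying of which line.

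**The case against.** The strongest reply is that the protocol chose description on purpose. It assigns tests to TTPP1, time to 50% PSA decrease, TTF1 and rPFS, and leaves TTPP2 and TTF2 descriptive. The SAP follows that choice, and omitting one sentence changes no analysis. A Cox hazard ratio is also missing for TTF1 and time to 50% PSA decrease. This stands as a reason not to add a hypothesis test. It does not exclude an effect estimate with an interval, which is itself descriptive, and TTF1 and time to 50% decrease at least have a stratified log-rank comparison.

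It is also true that the whole Kaplan–Meier distribution is estimated in each group, that groups are already defined as sequences, and that SAP 7.8 repeats the TTPP2 analysis by disease stage. A reader is therefore not confined to comparing two medians, and the plan prescribes no rule about overlapping intervals. None of this supplies an adjusted contrast or its uncertainty.

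Finally, precision would be limited, and a TTPP2 hazard ratio would be ill defined until the conflicts in step 5 are resolved. Both points stand, and they shape the fix.

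**Conclusion.** The gap is real and lies in the planned analysis. Two secondary objectives ask about order, and neither endpoint has a between-sequence estimate or interval.

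A reader might go further and infer that the switching design cannot answer the order question. The documents do not support that. Subjects are randomized 1:1 to two sequences, with the switch triggered mainly by progression. This is not a within-patient crossover, and a randomized comparison from randomization is available for TTF2 as the plan stands.

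Over an assumed 80 to 150 events, the interval would be the hazard ratio multiplied or divided by about 1.55 to 1.38. This rests on equal allocation of events and proportional hazards; the event range is not from the documents. For TTPP2 the upper end looks optimistic. Moderate order effects could remain inconclusive after the change, but the trial would report their size and uncertainty. This is a worthwhile, inexpensive improvement and not a threat to the primary result.

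**What to change.** **SAP 7.4.2.6 (TTF2), now.** Add a hazard ratio (enzalutamide-first over flutamide-first) with 95% CI from the Cox model already specified for TTPP1, with disease stage (M0/N0, M0/N1, M1) as a covariate; stratifying by stage would serve equally well. Add the between-sequence difference in Kaplan–Meier proportions at 12 and 24 months, each with 95% CI. State that no hypothesis test is performed.

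**SAP 7.4.2.1 (TTPP2), after reconciliation.** Align the start date across Protocol 7.4.2.1 and SAP 7.4.2.1. Randomization is the origin that keeps the contrast randomized. State whether the switch gap counts, and remove or explain the total-of-two-times wording. State in Table 7-1 which line's discontinuation censors TTPP2, including for subjects who switch without PSA progression. Then add the same estimates as for TTF2.

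**Both sections.** Restore the protocol's statement that the comparison is descriptive.

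**Cost.** A few lines of text, one model and two differences per endpoint. No new data are needed and no alpha is spent. The hazard ratio assumes proportional hazards, which is why the fixed-time differences accompany it. If the SAP is not amended, SAP 1 allows the change to be justified in the clinical study report.

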5.3.1.1 Time to PSA Progression with 1st Line AAT (TTPP1)

PSA progression will be defined according to the consensus guidelines of PCWG2. For patients with PSA declines at Week 13, the PSA progression date is defined as the date that a $\geq 25\%$ increase and an absolute increase of ≥ 2 ng/mL above the nadir is documented, which is confirmed by a second consecutive value obtained 3 or more weeks later. For patients with no PSA decline at Week 13, the PSA progression date is defined as the date that a $\geq 25\%$ increase and an absolute increase of ≥ 2 ng/mL above the baseline is documented.

TTPP1 is defined as the period from the date of randomization to the date of PSA progression in the 1st line AAT period.

5.3.1.2 Time to PSA Progression with 1st Line AAT + 2nd Line AAT (TTPP2)

Time to PSA progression with 2nd line AAT is defined as the period from Day 1 of 2nd line AAT to the date of PSA progression with 2nd line AAT. TTPP2 will be the total of time to PSA progression with 1st line AAT and time to PSA progression with 2nd line AAT.

5.3.1.3 PSA Response Rate to 1st Line AAT (Decrease by at Least 50% or 90% from Baseline)

PSA response will be defined as PSA decreased by at least 50% or 90% from baseline when at least 3 weeks passed after the lowest PSA decreased by at least 50% or 90% from baseline in the 1st line AAT period after baseline. The proportion of the subjects who achieved PSA response will be evaluated.

5.3.1.4 PSA Response Rate to 1st Line AAT at Week 13 (Decrease by at Least 50% or 90% from Baseline)

PSA response will be defined as the lowest PSA at Week 13 decreased by at least 50% or 90% from baseline in the 1st line AAT period. The proportion of the subjects who achieved PSA response will be evaluated.

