7.4.3.2 PSA Response Rate to 2nd line AAT

The PSA response rate to 2nd line AAT will be assessed by the same method as that with the PSA response rate to 1st line AAT.

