6.1.2 Secondary Efficacy Endpoints

Time to PSA progression with 1st line AAT + 2nd line AAT (TTPP2)

Time to PSA progression with 2nd line AAT is defined as the period from Day 1 of 2nd line AAT to the date of PSA progression with 2nd line AAT. TTPP2 will be the total of time to PSA progression with 1st line AAT and time to PSA progression with 2nd line AAT.

PSA response rate to 1st line AAT (decrease by at least 50% or 90% from baseline)

PSA response will be defined as PSA decreased by at least 50% or 90% from baseline when at least 3 weeks passed after the lowest PSA decreased by at least 50% or 90% from baseline in the 1st line AAT period after baseline. The proportion of the subjects who achieved PSA response will be evaluated.

PSA response rate to 1st line AAT at Week 13 (decrease by at least 50% or 90% from baseline)

PSA response will be defined as the lowest PSA at Week 13 decreased by at least 50% or 90% from baseline in the 1st line AAT period. The proportion of the subjects who achieved PSA response will be evaluated.

Time to PSA decrease by 50% from baseline with 1st line AAT

Time to PSA decrease by 50% with 1st line AAT is defined as the period from the date of randomization to the day when the decrease of PSA from baseline by 50% is first identified.

Time to treatment failure of 1st line AAT (TTF1)

Time to treatment failure is defined as the period to study drug discontinuation for any reason that includes disease progression, onset of AEs, subjects' request, or death. The following will be evaluated.

The period from randomization to discontinuation of 1st line AAT will be evaluated.

Time to treatment failure of 2nd line AAT (TTF2)

The period from randomization to discontinuation of 2nd line AAT will be evaluated.

rPFS

Imaging examination will be performed with chest CT, abdominopelvic CT or magnetic resonance imaging (MRI), and bone scintigraphy in the screening period, at study visit every 12 weeks after Week 1 (Day 1) of 1st line AAT irrespective of switching the drugs, and at

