7.4.3 Analysis of Exploratory Endpoints

7.4.3.1 Time to PSA Progression with 2nd Line AAT (2nd TTPP)

2nd TTPP is defined as the period from the start of 2nd line AAT to the first day when PSA progression is objectively identified. Convention of censoring is specified in Table 7-1.

The 2nd TTPP will be assessed by the same method as that with the Time to Treatment Failure of 2nd Line AAT (TTF2).

7.4.3.2 PSA Response Rate to 2nd line AAT (Decrease by at Least 50% or 90% from Baseline)

The PSA response rate to 2nd line AAT decreasing by at least 50% (or by at least 90%) will be calculated by treatment groups of subjects with baseline PSA value and PSA measured at least once at least 3 weeks passed after the lowest PSA. The PSA response rate to 2nd line AAT will be assessed by the same method as that with the PSA response rate to 1st line AAT.

Water fall plot will be made to present the percent change of PSA from baseline at the lowest PSA value (except within 3 weeks from baseline) for patient who have at least one time point PSA reduction in the 2nd line AAT period, and the highest PSA value (except within 3 weeks from baseline) for patient who have never had PSA reduction, respectively.

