Screening visit	−28 days to −7 days	28 days to 7 days before randomization
Week 1 (Day 1)	1	-
Week 5 (Day 29)	29	Reference date \pm 7 days
Week 9 (Day 57)	57	Reference date \pm 7 days
Week 13 (Day 85)	85	Reference date \pm 7 days
Every subsequent 4 weeks	Every subsequent 28 days	Reference date ± 7 days

2nd line AAT

Study Visit	Reference Date	Acceptable Range
Week 1 (Day 1)	1	-
Week 5 (Day 29)	29	Reference date \pm 7 days
Week 9 (Day 57)	57	Reference date \pm 7 days
Week 13 (Day 85)	85	Reference date \pm 7 days
Every subsequent 4 weeks	Every subsequent 28 days	Reference date ± 7 days
At completion or discontinuation	Day of completion or discontinuation visit	Reference date + 7 days
Safety follow-up	Final study treatment + 28 days	Reference date ± 7 days

The value which assessment day is the closest to the defined target day within these windows is used. If two values are equally close, the earlier is used in the analysis. Note that a value which is assessed prior to Day 1 of the 1st line AAT or 2nd line AAT will be available as baseline assessment once it is investigated and approved by the review board. Also, a value which is assessed as Day 1 of the 2nd line AAT will be utilized as end/discontinuation of 1st line AAT when a subject start 2nd line AAT without confirmation of PSA progression or because of other than PSA progression.

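### The SAP's denominator for PSA response removes subjects whom the protocol counts as non-responders

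*SAP*

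**What the plan says.** Protocol 7.4.2.2 and the protocol synopsis calculate the response rate among "subjects with baseline PSA value and PSA measured at least once after baseline". Protocol 7.4.3.2 states that the 2nd line rate "will be assessed by the same method as that with the PSA response rate to 1st line AAT".

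SAP 7.4.2.2 calculates the 1st line rate among "subjects with baseline PSA value and PSA measured at least once at least 3 weeks passed after the lowest PSA". SAP 7.4.3.2 carries the same requirement for 2nd line: "PSA measured at least once at least 3 weeks passed after the lowest PSA". The SAP does not identify this as a change. Its introduction presents it as a more detailed account of the protocol analysis, and its revision history lists only version 1.00.

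The responder definition is the same in both documents and already includes the timing condition. Protocol 5.3.1.3 recognises a decrease "when at least 3 weeks passed after the lowest PSA decreased by at least 50% or 90% from baseline". SAP 6.1.2 keeps the condition, with the 3 weeks counted "after the lowest PSA decreased by at least 50% or 90% from baseline in the 1st line AAT period after baseline".

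The subset defined in SAP 7.4.2.2 feeds the stratified Cochran-Mantel-Haenszel tests, the Clopper-Pearson intervals and the Mantel-Haenszel risk difference. The two-sided 0.05 level is stated there for the 90% comparison and is the general default in SAP 7.1.1.

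**The concern.** Once confirmation at 3 weeks is required to be a responder, requiring a 3-week value to enter the denominator as well can only remove failures. Subjects whose later PSA fails to confirm the decrease stay in as non-responders. Subjects who have no later PSA disappear.

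Whether such a value exists depends on when the lowest PSA falls and whether a later 1st line PSA was taken. Both are settled after randomization and may differ between arms; the protocol itself assumes median TTPP1 of 10.5 v 6 months. The tested comparison then no longer follows the protocol rule, and both the rates and the risk difference can shift for reasons unrelated to response.

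**Working it through.** **Plan's own figures.** The documents give no expected PSA response rate and no sample size for this endpoint. The only sizing is for TTPP1, and it reproduces. With HR = 6/10.5 = 0.571, two-sided 0.05 and 90% power, the Schoenfeld formula gives 134.2, rounded up to 135 events. The plan's event probabilities are 0.858 and 0.966 (mean 0.912), so 135/(2 × 0.912) = 73.99, or 74 per group. Changing the response denominator does not touch these figures.

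**Who is treated differently.** For a subject with a baseline PSA and at least one later PSA:

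| Subject | Protocol | SAP |
|---|---|---|
| PSA at least 3 weeks after the lowest, decrease confirmed | responder | responder |
| PSA at least 3 weeks after the lowest, not confirmed | non-responder | non-responder |
| No PSA at least 3 weeks after the lowest | non-responder | excluded |

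Only the third row changes. Two groups can fall in it.

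1. Subjects with no decline at Week 13 who progress and have no later 1st line PSA. Protocol 5.3.1.1 asks for no second value here: "For patients with no PSA decline at Week 13, the PSA progression date is defined as the date that" the threshold rise above baseline is documented. Some or all may be retained. By the protocol's key terms the 1st line period can run to the start of the second drug, which may be up to 6 weeks after progression and is first taken the day after prescription (protocol 5.1.5). Under SAP 7.11.3, when the switch is made without confirmed PSA progression or for another reason, "a value which is assessed as Day 1 of the 2nd line AAT will be utilized as end/discontinuation of 1st line AAT". A discontinuation or unscheduled PSA may also serve. If the lowest PSA may be the Day 1 value, a subject whose PSA never fell has Day 1 as his lowest, and Week 13 is 12 weeks later, so he stays in. The denominator sentence does not say.
2. Subjects whose last 1st line PSA is below baseline and is their lowest. These are lost under either reading of the lowest PSA.

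**Effect on a rate.** With n subjects under the protocol rule, r responders and a share e excluded (all non-responders), the SAP rate is r/(n(1 - e)), which is the protocol rate divided by (1 - e). It never falls. A 40% rate becomes 42.1%, 44.4% and 47.1% at e = 5%, 10% and 15%. With equal e in both arms the ratio of rates is unchanged and the difference grows by 1/(1 - e).

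**Effect on the comparison.** Responder counts and exclusions below are assumptions; the documents supply neither. There are 100 subjects per arm and the test is an unstratified two-proportion z test with pooled variance.

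| Responders (enz v flu) | Excluded (enz/flu) | Rates | Difference | p |
|---|---|---|---|---|
| 40 v 26 | 0/0 | 40.0% v 26.0% | 14.0 points | 0.035 |
| 40 v 26 | 5/15 | 40/95 = 42.1% v 26/85 = 30.6% | 11.5 points | 0.11 |
| 40 v 26 | 15/5 | 40/85 = 47.1% v 26/95 = 27.4% | 19.7 points | 0.006 |
| 40 v 26 | 10/10 | 40/90 = 44.4% v 26/90 = 28.9% | 15.6 points | 0.030 |
| 60 v 40 | 0/0 | 60.0% v 40.0% | 20.0 points | 0.005 |
| 60 v 40 | 5/15 | 60/95 = 63.2% v 40/85 = 47.1% | 16.1 points | 0.030 |
| 60 v 40 | 15/5 | 60/85 = 70.6% v 40/95 = 42.1% | 28.5 points | 0.0001 |

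The single-stratum Cochran-Mantel-Haenszel statistic leads to the same conclusions.

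**Type I error.** This was simulated with equal protocol rates of 40% and 100 per arm. The SAP denominator rejects about 5% of the time with 5% excluded in both arms, 10.3% with 5% v 15%, and 30.8% with 5% v 25%.

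**The case against.** The strongest objection is that the responder sentence is awkward and could mean 3 weeks from the first qualifying fall, not from the lowest value; the secondary objective counts a decrease whatever its timing. On that reading a subject still falling at his last visit may be a protocol responder whom the SAP drops. The rate could then fall: 40/100 with five such responders removed is 35/95 = 36.8%. That reading has to pass over the words about the lowest PSA, which stand in both the definition and the SAP denominator. If it were right, the SAP denominator would be removing genuine responders, so restoring the protocol denominator would still be correct. What stands is that the one-way effect on the rate holds for the text as written.

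Second, the excluded group may be small. Subjects who decline by Week 13 and later progress are retained, because progression from nadir needs a second value at least 3 weeks after the first rise. The safety follow-up PSA might also count for some who stop, though its assignment to 1st line is not stated. This stands: it limits the likely size, and the tables are not estimates.

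Third, the large swings come from a chosen threefold imbalance in exclusions; with 10 excluded in each arm, p moves only from 0.035 to 0.030. That also stands.

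Fourth, the protocol denominator also requires a post-baseline PSA, first scheduled at Week 13, so it too is not fully ITT. That is true, but the SAP adds a further and more selective condition.

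Finally, the Week 13 rate keeps the protocol denominator, and time to PSA decrease by 50% is tested in the ITT population. These analyses limit the consequence but do not correct the affected rate.

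**Conclusion.** The concern holds. Without explanation, the SAP replaces the protocol denominator for a tested secondary endpoint and for the matching exploratory 2nd line endpoint. On the definitions as written, everyone it removes is a protocol non-responder, so each arm's rate can only stay the same or rise, by 1/(1 - e). The between-arm bias depends on how e differs between arms, and neither its direction nor its size can be determined from the documents. In the assumed cases above, a 14.0-point difference becomes 11.5 or 19.7 points, and significance can be lost at moderate effects. Larger effects keep significance, but the reported rates and risk difference still move. The primary TTPP1 analysis, the sample size and the Week 13 response rate are unaffected.

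**What to change.** In SAP 7.4.2.2, restore the protocol denominator: a baseline PSA and at least one post-baseline PSA. Apply the same rule in 7.4.3.2 with the 2nd line baseline. Keep the 3-week condition in the responder definition only, so that subjects without a later PSA count as non-responders. Report the rate among subjects with the later PSA as a sensitivity analysis, with the number excluded by arm and reason. State whether the lowest PSA excludes the Day 1 value.

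The cost is a change of SAP wording and one reprogrammed flag. Reported rates will be slightly lower. Subjects whose PSA is still falling at the last measurement count as non-responders, as they already do under the protocol text. That could weigh more on the arm with longer PSA control, and the sensitivity analysis would show by how much.
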